9.4 Allocation of Subjects to Treatment

Subjects will be randomly assigned a 4-digit randomisation number beginning by "1", "2", "3", "4", "5" and "6" for Cohorts 1, 2, 3, 4, 5 and 6 respectively. Each subject number corresponds to a treatment assignment on the generated randomisation scheme.

For Part 1 (healthy adults), the two sentinel subjects of each cohort will have the first two subject numbers of their cohort e.g. 1001 and 1002 for Cohort 1, and 2001 and 2002 for Cohort 2 and 3001 and 3002 for Cohort 3. In the case where a subject is replaced (following specifications described in Section 9.13), the replacement volunteer will take the same treatment and the same subject number added with 100. For example, if the subject number 1001 withdrew, the replacement subject will have the subject number 1101, with the treatment planned for the randomization number 1001.

For Part 2 (healthy older adults), subjects will be randomly assigned to treatment groups in a 3:1 ratio of Active to Placebo. The randomisation will be stratified by age (≥ 56 to ≤ 65 years, and ≥ 66 years respectively).

For subjects who are replaced, the replacements should take the same treatment assignment as the original subject to ensure that the planned treatment allocation ratio is retained.

9.5 Study Medication

Drug Product (DP) will be provided as separate single-use vials containing each, the SARS-CoV-2 Sclamp antigen (CSIRO Manufacturing, Clayton VIC 3168, Australia). Squalene adjuvant material, MF59C.1, will be supplied in pre-filled syringes each containing a total volume of 0.25 mL (Seqirus). DP and adjuvant will be mixed at the clinical site, and 0.5 mL of the vaccine

suspension will be drawn into a syringe for IM injection as the final investigational medicinal product (IMP).

Placebo will be provided in a single-use vial containing sterile saline for injection (Pfizer, Mulgrave VIC 3170). 0.5 mL of the placebo will be drawn into a syringe for injection.

All vaccine and placebo materials will be received and handled while observing aseptic techniques. After preparation, the vaccination dose will be transported in a blinding bag placed in a box, and unblinded dosers will be used to preserve the blinding, as physical masking of the syringe to preserve the blind is not possible.

Subjects will receive two single IM doses (5, 15, or 45 mcg) of the following 3 study treatments at 28 days apart as follows:

- Treatment A (Cohorts 1 & 4): SARS-CoV-2 Sclamp vaccine 1 x 5 mcg in 0.5 mL suspension, or placebo, administered in a two dose regimen at least 28 days apart.
- Treatment B (Cohorts 2 & 5): SARS-CoV-2 Sclamp vaccine 1 x 15 mcg in 0.5 mL suspension, or placebo administered in a two dose regimen at least 28 days apart.
- Treatment C (Cohorts 3 & 6): SARS-CoV-2 Sclamp vaccine 1 x 45 mcg in 0.5 mL suspension, or placebo administered in a two dose regimen at least 28 days apart.
- Treatment D (Cohort 3 only): SARS-CoV-2 Sclamp vaccine 1 x 45 mcg in 0.5 mL suspension, or placebo administered as a single dose, followed by placebo as the second dose, at least 28 days apart.
- Placebo: 0.5 mL solution (Sterile saline for injection)

9.6 Treatment Supplies and Accountability

It is the responsibility of the Sponsor to ensure that the study vaccine, adjuvant and placebo provided for this study are suitable for human use. The active vaccine and placebo products will be provided by the Sponsor, packed and labelled in accordance with GMP and Annex 13 requirements. The Sponsor is responsible for shipping a sufficient amount of dosage units to allow the clinical site to maintain an appropriate sampling for the study, according to TGA regulation.

Study medication will be stored at the clinical site as per applicable requirements. SARS-CoV-2 Sclamp antigen will be stored in a locked, environmentally-controlled medication room (at 2-8 °C) with restricted access, and the MF59C.1adjuvant will be stored in a locked, environmentally-controlled medication room (at 2-8 °C) with restricted access. The individual dosage units and outer container(s) will bear a label containing at least the name of the study treatment, lot and/or batch number, and manufacturing and/or expiry/retest date. The management of investigational vaccines is under the supervision of the Investigator.

Individual doses for each subject and period will be dispensed at the clinical site, as per the appropriate local SOP. Individual doses will be dispensed according to the randomization scheme in appropriate containers indicated with at least the project number and the subject number. Whenever possible, dispensing and study treatment administration should be conducted within 3

hours of preparation of each dose, which will be stored at ambient temperature in a locked medication room prior to use. If stored refrigerated, syringes must be allowed to acclimatise to room temperature for at least 10 minutes prior to use.

All study vaccine materials received at the clinical site will be inventoried and accounted for throughout the study, and the result recorded in the drug accountability/retention record according to the clinical site appropriate SOP. Upon completion of the study, the remaining test and reference products will be maintained at the clinical site, discarded or returned to the Sponsor, as per Sponsor's request.

9.7 Study Treatment Administration

The study vaccine, or placebo, will be administered to the deltoid region of the subjects non-dominant arm(or deltoid region of other arm should a tattoo be present) via IM injection observing aseptic techniques. Detailed instructions for study vaccine administration will be included in the pharmacy manual.

Prior to treatment administration, subjects must be determined to be eligible for study vaccination and it must be clinically appropriate in the judgement of the Investigator, or another attending study physician, to vaccinate. Eligibility for study treatment administration prior to first administration is determined by evaluating the eligibility criteria outlined in Sections 8.3 and 8.4. For second dosing (Day 29), subjects who may fall outside of the bounds of eligibility criteria may still be dosed if it is deemed safe to continue in the opinion of the Investigator, or other attending study physician. Those subjects who fall outside the bounds of eligibility and who are not dosed will be withdrawn from the study and the reason for discontinuance documented.

Standard immunisation practices are to be observed, and care should be taken to administer the injection intramuscularly. Before administering vaccine, the vaccination site is to be disinfected with an appropriate skin disinfectant (e.g. 70% alcohol) and allowed to dry.

As with all injectable vaccines, trained medical personnel and appropriate medical interventions should be readily available in case of anaphylactic reactions following vaccine administration e.g. adrenaline (epinephrine), diphenhydramine, and/or other medications for treating anaphylaxis should be available).

The time of injection of each subject will be recorded in the source documents. Time of dosing will be set as the time of start of injection.

9.8 Study Restrictions

9.8.1 Food and Fluids

No food or fluid intake restrictions will be in place for the duration of the study.

9.8.2 Tobacco, Alcohol, and Illicit Drugs

Subjects will be required to abstain from using soft or hard drugs from screening and throughout the study or any tobacco or nicotine products from at least 2 hours prior to each dosing until 4 hours post-dose. Subjects will be required to abstain from food containing poppy seeds within 24 hours prior to each treatment administration.

Consumption of alcohol-based products will be prohibited from 24 hours prior to each visit on Days 1, 2, 8, 15, 29, 30, 36, 43, 57, 209, and 394.

9.8.3 Prior and Concomitant Medications

Subjects will be required to avoid using excluded prescription, over-the-counter (OTC) (other than those specified in the protocol), immunosuppressant treatments and related coronavirus vaccines i.e. SARS-CoV-1, SARS-CoV-2, MERS-CoV etc. for the periods of time specified in exclusion criterion #11 and throughout the study.

All medications and vaccinations taken by subjects after screening until the last study day will be documented as concomitant medications. Concomitant medications will be documented by treatment group, therapeutic area, and preferred drug name. Additionally, prior medical history of vaccinations, especially recent history of immunization boosters or influenza vaccinations, may be categorized as concomitant medications. If it is unclear whether a subject's use of medication is to be classified as a prior or concomitant medication i.e. falling within the screening period or periods of time specified in exclusion criterion #11, it is to be assumed that its use is concomitant.

Medications will be coded using the WHO Drug dictionary, and a listing will be presented for all concomitant medication data for all subjects.

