Study Day (Visit window)	Day -28 to Day -1	Day 1	Day 2 ⁴	Day 8 (±1 day)	Day 15 (±1 day)	Day 29 (±2 days)	Day 30 ⁴ (±2 days)	Day 36 (±2 days)	Day 43 (±2 days)	Day 57 (±2 days)	Day 120 (+20 days)	Day 209 (±5 days)	Day 394 (±5 days)	Ad Hoc
Informed consent	X													
Review of Subject Eligibility	X	X ⁵												
Medical History	X													
Demographics (sex and race) and baseline characteristics including previous vaccination status	X													
Physical Examination	X	X ⁶				X ⁶								
Height, Weight, BMI	X													
SARS-CoV-2 Test ⁷	X	X				X								
Serology (HIV, Hepatitis B and C)	X													
Injection site assessment ⁸	X	X	X	X		X	X	X						(X) ⁹

Visit Type	Screening	Visit 1	Visit 2	Visit 3	Visit 4	Visit 5 ¹	Visit 6	Visit 7	Visit 8	Visit 9	Visit 10 ¹⁸ *(Cohorts 1-2 only)	Visit 11 ²	Visit 12 ²	Ad Hoc Visit
		First Dose	Safety	Safety/ Immunol.	Immunol.	Second Dose ³ / Immunol.	Safety	Safety/ Immunol.	Immunol.	Immunol.	3-4 month follow-up	6-month follow-up	12-month follow-up / EOS	Unscheduled Visit / Early Termination
Study Day (Visit window)	Day -28 to Day -1	Day 1	Day 2 ⁴	Day 8 (±1 day)	Day 15 (±1 day)	Day 29 (±2 days)	Day 30 ⁴ (±2 days)	Day 36 (±2 days)	Day 43 (±2 days)	Day 57 (±2 days)	Day 120 (+20 days)	Day 209 (±5 days)	Day 394 (±5 days)	Ad Hoc
Vital Signs Measurements (BP, HR, RR, TT and Oxygen Saturation (SpO ₂))	X	X	X			X	X							
Serum Pregnancy Test (females)	X	(X) ¹⁰				(X) ¹⁰								
Urine pregnancy test(females)		X				X								
FSH test (to confirm menopausal female)	X													
Subject Dosing		X				X								
ECG	X	X	X			X	X							
Urinalysis	X	X	X	X		X	X	X		X				X
Post dose Monitoring ¹¹		X	X	X		X	X	X						
Training for Electronic Diary Completion		X												
Review of Diary entries ¹²				-----X-----										X
Electronic Diary Entry ¹³				-----X-----										
Concomitant Medications	X	X	X	X	X	X	X	X	X	X				X
Adverse events ¹⁴	X			-----X-----										X
Urine Drug Panel	X	X				X								

Visit Type	Screening	Visit 1	Visit 2	Visit 3	Visit 4	Visit 5 ¹	Visit 6	Visit 7	Visit 8	Visit 9	Visit 10 ¹⁸ *(Cohorts 1-2 only)	Visit 11 ²	Visit 12 ²	Ad Hoc Visit
		First Dose	Safety	Safety/ Immunol.	Immunol.	Second Dose ³ / Immunol.	Safety	Safety/ Immunol.	Immunol.	Immunol.	3-4 month follow-up	6-month follow-up	12-month follow-up / EOS	Unscheduled Visit / Early Termination

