10. Participation in a clinical research study involving the administration of an investigational, or marketed, drug or device within 30 days prior to receiving the first treatment administration, or administration of a biological product in the context of a clinical research study within 90 days prior to the first dosing, or concomitant participation in an investigational study involving no drug, vaccine, or device administration, or intent to participate in another clinical study at any time during the conduct of the study.
11. Use of medications for the timeframes specified below, with the exception of hormonal contraceptives and medications exempted by the Investigator on a case-by-case basis because they are judged to interfere with subject safety e.g., topical drug products without significant systemic absorption are permissible:
 - a. Prescription medication within 14 days prior to the first dosing;
 - b. Any medication, or treatments, that may affect the immune system such as allergy injections, immunoglobulin, interferon, immunomodulators, cytotoxic drugs, or other drugs known to be frequently associated with significant major organ toxicity within 90 days prior to enrolment;
 - c. Any registered vaccine administered within 30 days prior to enrolment in the study, or who plan to receive any non-study vaccines within 28 days of the second dose of the study vaccine

- d. Any other investigational coronavirus vaccine i.e. SARS--CoV-1, SARS--CoV-2, MERS etc. at any time prior to, or during, the study.
 - e. Over-the-counter products within 7 days prior to the first dosing, with the exception of the occasional use of paracetamol (up to 2 g daily) and standard dose vitamins.
12. Donation of plasma within 7 days prior to dosing. Donation or loss of blood (excluding volume drawn at screening) of 50 mL to 499 mL of blood within 30 days, or more than 499 mL within 56 days prior to the first dosing.
 13. Receipt of blood products within 2 months prior to the first study treatment administration (Day 1), or planned receipt of blood products during the study period.
 14. Breast-feeding subject, or subject who plans to breastfeed from the time of first dose through 60 days after last study treatment administration.
 15. Presence of tattoos, scarring, skin discoloration, or any other skin disturbances at the injection site which, in the opinion of the Investigator, may inhibit the ability to effectively perform an injection site assessment.

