11.4.2 Safety Population

Includes all trial subjects that:

- Provide consent; and
- Are randomized; and
- Receive at least one dose of the study treatment, and
- Provided any evaluable safety data.

The Safety Population will be used for all safety analyses and will be analysed as actually treated.

11.4.3 Immunogenicity Population up to Day 57

Includes all subjects in the Safety Population that:

- Have immunological results for Days 1, 15, 29, 36, 43, and 57 (subjects who withdraw early and do not complete all assessment days will still be included for analyses); and
- Did not experience a laboratory confirmed COVID-19 illness between Day 1 and Day 57; and
- Did not receive any prohibited medication during the study to Day 57 that is medically assessed to potentially impact the immune response (and immunogenicity results); and
- Have no major protocol deviations affecting the primary immunogenicity outcomes as determined by the Sponsor prior to database lock and unblinding.

The Immunogenicity Population will be the primary population used for immunogenicity analyses for the Day 57 analyses for each of Part 1 and Part 2.

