11.4.4 Full Immunogenicity Population

Includes all subjects in the Immunogenicity Population that:

- Have also completed follow-up examinations on Days 209 and 394; and
- Did not experience a laboratory confirmed COVID-19 illness between Day 1 and Day 394.

The Full Immunogenicity Population will be the primary population used for follow-up analyses.

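### After Day 57 no planned visit has a medication or vaccination review marked, and the Day 209/394 population has no rule to set aside samples drawn after another coronavirus vaccine

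*Protocol*

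**What the plan says.** Section 9.8.3 sets the recording rule: "All medications and vaccinations taken by subjects after screening until the last study day will be documented as concomitant medications". The same section has subjects avoid "immunosuppressant treatments and related coronavirus vaccines i.e. SARS-CoV-1, SARS-CoV-2, MERS-CoV etc" for the periods in exclusion criterion 11 and throughout the study.

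Criterion 11d in Section 8.4 is worded differently: "Any other investigational coronavirus vaccine i.e. SARS--CoV-1, SARS--CoV-2, MERS etc. at any time prior to, or during, the study". Criterion 11c excludes those "who plan to receive any non-study vaccines within 28 days of the second dose of the study vaccine".

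In the Schedule of Events (Section 4), the row "Concomitant Medications" is marked at Screening, at Visits 1 to 9 (Day 1 to Day 57) and in the ad hoc/early termination column. It is blank at Visit 10 (Day 120), Visit 11 (Day 209) and Visit 12 (Day 394).

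Section 11.4.3, which defines the Immunogenicity Population up to Day 57, requires that a subject "Did not receive any prohibited medication during the study to Day 57", limited to medication judged able to affect the immune response. Its deviation criterion concerns the primary immunogenicity outcomes. Section 11.4.4 builds the Full Immunogenicity Population on that set and adds two conditions: completion of Days 209 and 394, and "Did not experience a laboratory confirmed COVID-19 illness between Day 1 and Day 394". This is the primary population for follow-up analyses.

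**The concern.** Two parts of the protocol that should protect the late titres stop at Day 57. The text asks for a complete medication and vaccination history to study end, but no planned visit after Day 57 is set up to obtain it. The follow-up population was extended to deal with one later source of antibody, infection, but not with another, non-study vaccination, nor with drugs that alter the immune response.

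At stake are the GMT and the proportion with at least a 4-fold rise, each against placebo, at Days 209 and 394. These are secondary endpoints in Section 5.4. The protocol gives reason to think the exposure plausible. The Synopsis expects the last 12-month assessments in November 2021, Section 5.1 describes worldwide vaccine development, and Section 8.1 selects the Part 2 subjects because older adults are at greatest risk. The study antigen is Spike and the neutralisation assay uses SARS-CoV-2 virus, so another Spike-based vaccine would be expected to raise both measured titres.

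The direction differs by arm. In a vaccine arm, outside vaccination makes persistence look better than it is. In placebo, it raises the comparator and shrinks the vaccine/placebo contrast. The net effect depends on how such exposure falls across arms. An immune-modifying drug could distort titres too, in a direction that depends on the drug.

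**Working it through.** The protocol gives no figure for this point to reproduce, and Section 8.2 states that no power calculation was made. The check is a comparison of passages, followed by a labelled illustration.

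**1. Recording rule against visits.** The Schedule has 14 columns: Screening, Visits 1 to 12, and ad hoc. The concomitant-medication row fills all 14 cells, with 11 marked and 3 blank. The blanks are Days 120, 209 and 394. Two other sections agree with the blanks. The Day 394 exit procedures in Section 9.11 name blood draws and adverse event monitoring only. Section 9.14 does list a review of medications and vaccinations since the last visit, but only for subjects who terminate early. Completers have no matching item.

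**2. Length of the gap.**
- Days from Day 57 to Day 394: 394 − 57 = 337.
- Days after first dose: 394 − 1 = 393.
- Share: 337 / 393 = 0.858, or 86%.

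**3. Population criteria, Day 57 set against follow-up set.**

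| Criterion | 11.4.3 | 11.4.4 |
|---|---|---|
| Confirmed COVID-19 | Day 1 to 57 | extended to Day 394 |
| Prohibited medication affecting response | to Day 57 | not extended |
| Major deviations | primary outcomes (Days 29 and 57) | not extended |
| Completion | results to Day 57, early withdrawals kept | Days 209 and 394 completed |

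Take a subject who receives another coronavirus vaccine on, say, Day 150 and attends Days 209 and 394 without confirmed COVID-19. The subject meets every listed condition. The result is the same whether or not the site knows of the vaccination. Section 11.5 refers to the Immunogenicity Population for all days including 209 and 394. Reading it that way does not help, because that set also stops at Day 57.

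**4. Illustration of size (assumed inputs).** If k of m placebo subjects have their titre multiplied by R, the placebo GMT is multiplied by R^(k/m). If R is at least 4 and those subjects would otherwise not have responded, seroconversion rises by k/m. The values of R and k are assumptions; m comes from Section 6, which gives 8 placebo subjects per cohort and so 3 × 8 = 24 per Part.

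| m | k | R = 4 | R = 16 | R = 64 | Seroconversion |
|---|---|---|---|---|---|
| 8 | 1 | 1.19 | 1.41 | 1.68 | +12.5 points |
| 24 | 1 | 1.06 | 1.12 | 1.19 | +4.2 points |
| 24 | 2 | 1.12 | 1.26 | 1.41 | +8.3 points |
| 24 | 6 | 1.41 | 2.00 | 2.83 | +25.0 points |

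If the vaccine arm is unaffected, the unadjusted vaccine/placebo GMT ratio is divided by the same factor. For one subject in a cohort's 8, the ratio falls to between 1/1.68 = 0.60 and 1/1.19 = 0.84 of its value.

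**The case against.** A reader might infer that a late vaccination would go undetected, or that nothing is collected for 86% of the study. The documents do not support that. Section 9.8.3 itself requires documentation to the end. Section 9.10.7 has subjects report medication use and doctor visits in the diary, and Schedule footnote 13 keeps the non-daily diary forms available for the whole study. Medically attended events run to Day 394 (Section 5.4), and Section 11.1 collects unscheduled GP visits to study completion. Section 9.15.2 has the diary reviewed and the subject interviewed about adverse events at each visit. The span of the diary-review and adverse-event rows in the Schedule cannot be read from the text version. The 86% therefore describes the absence of a scheduled prompt, not of all capture. These routes are still partial. Section 9.10.7 ties diary use after Day 57 to safety events, and a routine vaccination is neither an adverse event nor a reason for an unscheduled visit.

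A reader might also infer that the study permits other coronavirus vaccines in follow-up, or that every recipient must stay in the analysis. Neither follows. They are barred throughout, and Section 9.13 allows withdrawal for non-compliance or a significant deviation. A subject withdrawn before Day 394 would fail the completion condition in 11.4.4. But withdrawal is discretionary and requires that the event be known, so it reduces the gap without closing it.

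A third argument is that sample-level handling belongs in the SAP, which supersedes the protocol and is not shown. That has force for the detail of the rule. It does not reach the two things the protocol itself fixes, the visit schedule and the Day 57 cut-off in the criterion that the follow-up population inherits. A SAP can redefine a population but cannot recover information that the visits did not ask for. Study team members are also unblinded after Day 57 (Sections 5.2 and 9.3), so a rule written late would be written with treatment known.

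Finally, the affected endpoints are secondary, there are no formal hypotheses (Section 11.3), and the protocol gives no rate of outside vaccination. All of that stands and limits the weight of the point.

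**Conclusion.** The point holds as an internal contradiction plus an incomplete population definition. Section 9.8.3 and the Schedule disagree about Days 120, 209 and 394. Section 11.4.4, read as written, keeps a subject who receives another coronavirus vaccine or an immune-modifying drug after Day 57 and is not withdrawn, even when this is known.

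The size cannot be fixed from the documents. A reader who assumes high uptake and large titre rises can produce much bigger multiples, but neither input is in the protocol. What can be said is that placebo groups of 8 per cohort are sensitive. Under an assumed 4- to 64-fold rise, one subject moves the cohort's placebo GMT by a factor of 1.19 to 1.68 and seroconversion by 12.5 points. If placebo is pooled within a Part, one subject matters less (1.06 to 1.19, and 4.2 points). The primary Day 29 and Day 57 analyses are not affected. The change is worth making because it is cheap and the missing information may not be recoverable afterwards.

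**What to change.** 1. In the Schedule of Events, mark concomitant medication and vaccination review at Visits 11 and 12 for all subjects, and at Visit 10 for the Cohort 1 and 2 subset who attend. Add the same item to the exit procedures in Section 9.11. This brings both into line with Section 9.8.3.
2. In Section 11.4.4, carry the prohibited-medication criterion past Day 57 and apply it by sample. Samples drawn after a non-study coronavirus vaccine, or after medication assessed as affecting the immune response, are left out of the Day 209 and Day 394 analyses, and earlier samples from that subject are kept. A subject-level rule would needlessly drop a valid Day 209 sample from someone vaccinated after that visit.
3. Reconcile exclusion 11d, which names investigational coronavirus vaccines only, with Section 9.8.3, which refers to related coronavirus vaccines without that limit, so that what counts as prohibited is the same in both places.

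The cost is one question at visits already attended, a short addition to 11.4.4, and slightly fewer evaluable late samples.
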